4.3 Administration of Questionnaires to Patients

a. Patients will be assessed at baseline following consent, and at subsequent routine clinical visits (3, 6, 9 and 12 months) following registration. (See Section 5.0 for the list of questionnaires and time points they are to be administered.) Questionnaires will be self-administered and are anticipated to require 30 minutes to one hour to complete at each study time point.

- b. Target follow-up assessment dates should be based on the date of registration. A window of ± 21 days is allowed for each assessment to provide more flexibility in scheduling.
- c. Patients undergoing treatment for mCRC will generally be seen at the clinic or practice approximately every two weeks. In order to minimize patient burden and streamline patient visits, it is preferable for questionnaires to be given to the patient at the clinical visit immediately prior to the study time point, completed at home and returned at the routine clinical visit coinciding with the study time point; however, the study staff should accommodate the patient's preferences for filling out the questionnaires as described below. Some questionnaires will require detailed financial information so it is recommended that the CRA contact the patient a week before their scheduled visit to remind him/her to bring the appropriate information to the visit to complete the questions on the forms. At time of consent, the patient should be provided with a copy of the forms for reference.
- d. The research site should provide the patient with options for completing the questionnaires after the patient has reviewed them. The patient's review may help them decide if they need information they do not have with them at their visit or they may need assistance from a family member or caregiver. The patient may also be more comfortable completing the questionnaire(s) at home. The options for the patient are as follows:

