6.0 CRITERIA FOR EVALUATION AND ENDPOINT ANALYSIS

- 6.1 Primary Endpoint
 - a. Major Financial Hardship: Defined as one or more of the following during the 12 month study period: debt accumulation of any amount, selling or refinancing home, ≥ 20% income decline, borrowing money of any amount from family/friends.
- 6.2 Secondary Endpoints
 - a. Treatment Non-Adherence: Defined as refusing treatment or skipping doses due to cost concerns (e.g., lack of coverage, high co-payment requirement)

- b. Health-related Quality of Life (HRQOL): As measured by the EORTC Quality of Life Questionnaire C30 (QLQ-C30) v. 3.0. (14) This is a well-validated questionnaire which includes 30 items assessing global quality-of-life, functioning in five domains (physical, role, cognitive, emotional social) and several items assessing specific symptoms (e.g. fatigue, trouble sleeping, pain). Importantly, the QLQ-C30 does include one item assessing the impact of medical treatment on finances. Questionnaire responses will be transformed into a linear score (0 to 100) using the EORTC scoring manual.
- c. Out-of-Pocket Expenses: Defined as total out-of-pocket direct medical (e.g., prescriptions, physician visits, deductibles) and non-medical (transportation, meals) expenses in the 3 months prior to each study visit.
- d. Credit History (TransUnion): Credit reports are obtained at baseline, 6 months, and when the patient goes off protocol and measure the following: non-mortgage amounts past due on credit cards and bankcards; non-mortgage credit card and bankcard balances; bankruptcies, liens, collections or repossessions.

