A secondary objective of this study is to assess the relationship between major financial hardship and HRQOL. These factors are likely positively correlated and associated with the same general status of poor prognosis (endogenous factors). analysis that evaluates, from baseline, the association of major financial hardship and HRQOL will find a positive correlation as an artifact of the endogeneity, and adjustment for performance status is unlikely to fully account for this. Therefore we will use landmark analysis to establish major financial hardship as a baseline predictor of HRQOL. In particular, patients will be categorized as having major financial hardship at their 3 month assessment (yes vs. no). We will then use linear regression to assess whether the 3month assessment of financial hardship predicts the 6-month HRQOL score. HRQOL at 3 months will be included as an adjustment covariate. The 6-month HRQOL score will be based on the EORTC QLQ-C30 questionnaire transformed into a linear score (0 to 100) using the EORTC scoring manual. A difference in mean score of ≥ 10 between time points is considered clinically relevant. In addition, to assess the robustness of potential associations between major financial hardship and HRQOL to large changes in a subset of patients, HRQOL at 6 months will also be categorized as decline vs. no decline and logistic regression performed. This analysis is limited by the fact that patients without 6 months follow-up scores are more likely to be worse prognosis patients that may also be related to predictive factors of interest (that is, age, race, marital status, employment status, and income).

Feasibility

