The feasibility of successfully accruing to a prospective-multi-site longitudinal cohort study assessing financial outcomes in patients with metastatic colorectal cancer (mCRC) undergoing treatment within the NCORP network will be examined. The total anticipated accrual time is 3 years. To be conducted in that timeframe, each of the NCORP components (we anticipate 25 NCORP components) will each need to enroll, on average, about 5 patients per year. Accrual will be monitored regularly. Given the open eligibility criteria, we hypothesize that enrollment will be feasible. However accrual will be assessed at 1.5 years after study activation. If monthly average accrual in quarters 5-6 after study registration is < 50% of projected accrual, efforts will be made to increase accrual over the succeeding 6 month period. If after 2 years, monthly accrual remains < 50% of projected accrual, study revision will be considered. In order to address the potential for selection bias, we will compare demographics (age, race, gender, etc.) of the final cohort to the typical patient population seen at the various practice sites.

The feasibility of incorporating a caregiver component to the study will also be examined. Caregiver participation is optional. The caregiver component will be considered feasible if the designated caregivers for > 50% of eligible patients complete and submit their baseline and at least one follow-up assessment. We will use means, medians, proportions to describe the participating caregiver population. Our analyses will be largely descriptive. We will look at the proportion of caregivers who experienced changes in employment and expenses (caregiver questionnaire items 11 and 13). We expect that caregivers of patients who experience financial hardship will be more likely to report financial burden. We will therefore investigate the association between patient-reported financial hardship and level of caregiver-reported financial burden. We will compare proportion of caregivers experiencing 'high financial burden' (≥ 3 on Likert scale) for patients who do vs. do not report major financial hardship using two-sample t tests. If our caregiver accrual is very poor (<20%), we will focus on describing the patient population rather than attempting to correlate caregiver and patient responses.

7.3 Other Secondary Endpoints:

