The linkage of clinical and financial data with credit histories obtained from TransUnion will allow us to explore additional indicators of financial stress, including high balances

and past due amounts of credit card and bankcards as well as evidence of bankruptcies, liens, and collections or repossessions. These data will also allow us to corroborate self-reports of debt and bankruptcy in order to investigate the reliability of self-reports in estimating financial hardship. Credit reports will be obtained at baseline and at 6 and 12 months after registration. Given the poor 1-year survival for this patient cohort (60%), multiple post-baseline credit reports are requested to limit bias due to missing data related to death.

Other secondary objectives including measurement of out-of-pocket expenses, health insurance changes, changes in assets/income/wealth, measurement of debt and spending by credit report histories, and assessment of patient, caregiver, and bereaved caregiver financial stress will be handled using descriptive statistics (e.g. mean, median, proportions). We will use descriptive statistics to summarize baseline patient characteristics and will compare populations using two-sample means and proportions tests (α level 0.05). Caregiver strain index will be scored based on responses (score range 0 to 26). Mean scores will be compared for caregivers of patients reporting vs. not reporting at least one financial hardship.

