10.2 Administration of Questionnaires to Caregivers

- a. Caregivers will be asked to fill out the S1417CD Caregiver Questionnaire at baseline (following consent), and subsequently at 6 and 12 months following patient registration. The questionnaire will be self-administered and is anticipated to require a total of 30 minutes to complete at each study time point, by phone or by mail. The caregiver should be asked to complete the Caregiver Questionnaire even if the patient does not complete the patient questionnaires at the time point. Upon patient death, the caregiver's participation will discontinue and no further Caregiver Questionnaires are required.
- b. It is preferable for the caregiver to complete the Caregiver Questionnaire during the patient's routine clinical visits coinciding with the appropriate study time point; however, the study staff should defer to the caregiver's preferences for completing the questionnaires. Questionnaires may be done at home and mailed back to the research staff. Target follow-up assessments should be based on the date of patient registration. A window of ± 21 days is allowed for each assessment to provide more flexibility in scheduling.
- c. If the caregiver prefers to mail it back, the research site will provide a preaddressed stamped envelope. If the caregiver prefers to answer the questionnaire over the phone, research staff will make arrangements for a phone interview. When responses are obtained via phone interview, it is important that the caregiver is looking at a copy of the questionnaire while the staff conducts the interview. The date of the telephone interview is to be recorded on the Caregiver Questionnaire.
- d. It is very important to review the completed questionnaire with the caregiver during the clinic visit or over the phone to be sure all of the questions have been answered and, when the caregiver is directed to mark only one response, that

only one answer is marked. If the caregiver has marked more than one answer per question, ask them which answer reflects how he/she is feeling. If the caregiver has skipped a question, bring it to their attention and ask if they would like to answer the question. If the caregiver does not want to answer a particular question, the CRA will enter "Not answered by the caregiver" in Medidata $RAVE^{\otimes}$.

- 10.3 Criteria for Removal for Consented Caregiver from Study Participation
 - a. Caregiver completes 12 months of study participation.

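### Caregiver strain and burden are compared by patient hardship with no caregiver visit named, no cut-off for the hardship report, and no use of the baseline caregiver score

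*Combined protocol and SAP*

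**What the plan says.** Section 7.3 (Other Secondary Endpoints) scores the caregiver strain index from 0 to 26 and states: "Mean scores will be compared for caregivers of patients reporting vs. not reporting at least one financial hardship". Section 7.2, under Feasibility, compares the proportion of caregivers with high financial burden "for patients who do vs. do not report major financial hardship using two-sample t tests". The same paragraph says "Our analyses will be largely descriptive", but also states the expectation that caregivers of patients with hardship will report more burden. A sentence in Section 7.3 says the study will "compare populations using two-sample means and proportions tests (α level 0.05"); it does not say whether that level covers the caregiver comparisons.

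The timing of the two forms differs. Section 10.2 gives the caregiver form "at baseline (following consent), and subsequently at 6 and 12 months following patient registration", and stops it when the patient dies. Section 4.3 says: "Patients will be assessed at baseline following consent, and at subsequent routine clinical visits (3, 6, 9 and 12 months) following registration". The calendar in Section 5.0 gives the follow-up financial questionnaire from month 3. Section 6.1 describes major financial hardship as follows: "Defined as one or more of the following during the 12 month study period".

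For patient HRQOL, Section 7.2 notes that hardship and outcome may both reflect poor prognosis, and continues: "Therefore we will use landmark analysis to establish major financial hardship as a baseline predictor of HRQOL". Hardship is fixed at month 3, the outcome is the month-6 score, and the month-3 score is a covariate.

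**The concern.** Three things are left open in both caregiver comparisons: which of three caregiver scores is the outcome, which of four patient forms define hardship, and whether the baseline caregiver value enters. An analyst could settle all three after seeing the data.

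The 12-month definition in Section 6.1 makes any report during the year the natural reading. Under it, a patient who first reports hardship at month 9 or 12 counts as exposed for a caregiver score taken at month 6. To make that later report, the patient must also survive to the later form. Group membership then depends partly on survival after the outcome was measured. The plan expects 40% deaths at one year, so this could matter. The HRQOL analysis guards against it for the same exposure in the same cohort; the caregiver comparisons do not.

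At stake is the interpretation of the stated expectation about caregiver burden, not the primary endpoint.

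**Working it through.** **Inputs from the plan.** Deaths: 40% at one year, hazard 0.51 (Section 7.2). Hardship: 40% in the first year (Section 7.1), read here as a rate in the absence of death. Both exponential (Section 7.1). Other dropout: about 10% (Section 7.1). The plan gives no sample size, effect, SD or power for the caregiver comparisons.

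**The plan's own figure.** −ln(1 − 0.40) = 0.511, which reproduces 0.51.

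**Assumptions.** Hardship and death are independent. Hardship is reported at the next quarterly form if the patient is alive to complete it.

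**First reports after the month-6 caregiver form.** The probability of passing a quarter without hardship is 0.6^(1/4) = 0.8801, and the same holds for death. Among patients alive at month 6, without dropout:
- reported by month 6: 1 − 0.8801² = 0.2254
- first report at month 9: 0.8801² × 0.1199 × 0.8801 = 0.0817
- first report at month 12: 0.8801³ × 0.1199 × 0.8801² = 0.0633
- any report: 0.3704

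The late share is (0.0817 + 0.0633)/0.3704 = 39%. With 10% dropout, the month-9 and month-12 terms are multiplied by 0.9^(1/4) = 0.974 and 0.9^(1/2) = 0.949, giving 0.0796 and 0.0601. The late share is then 0.1397/0.3651 = 38%. If the hardship rate is 20% to 50% (the range of the precision table in Section 7.1), the share with dropout runs from 42% down to 36%.

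**Deaths in months 6 to 12, any-report grouping (no dropout).**
- Reporters: (0.2254 × 0.2254 + 0.0817 × 0.1199 + 0)/0.3704 = 0.0606/0.3704 = 16.4%
- Non-reporters: (0.2254 − 0.0606)/(1 − 0.3704) = 0.1648/0.6296 = 26.2%

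A simulation of 2 million patients gives 16.3% and 26.1%. Grouping by reports up to month 6 gives 22.5% in both groups. Under independence the gap therefore comes from the grouping alone.

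**Dependence on the independence assumption.** Multiplying both hazards by a shared gamma frailty with mean 1 (assumption) changes the picture. At variance 0.5, deaths in months 6 to 12 under any-report grouping are about 19% in both groups. At variance 1 the gap reverses, to about 21% of reporters against 15% of non-reporters. If hardship instead multiplies the death hazard by 1.75 (assumption), the figures are 26.3% and 26.8%. Grouping by month 6 does not equalise deaths in the frailty setting either: at variance 0.5 it gives about 26% against 18%. There the difference reflects the real link between hardship and prognosis, not later reports.

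**Possible size.** Under independence, and if caregivers of patients who die within the year score 1 SD higher (assumption), the month-6 difference with no true hardship effect is 0.163 − 0.261 = −0.10 SD. At month 12 it is zero, because every patient analysed is alive.

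**Gain from baseline adjustment.** At a baseline to follow-up correlation of 0.5 to 0.6 (assumption), it removes 0.5² to 0.6², or 25% to 36%, of the residual variance.

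**The case against.** The strongest reply has four parts.

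First, the any-report reading is an inference. Section 7.1 counts patients with one or more hardships at each study interval, so the phrase in Section 7.3 could mean one or more types of hardship at the same visit. That stands, and the 38% figure depends on the reading. But if the reading is wrong, the comparison is still undefined.

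Second, a reader might infer that patients who die early swell the no-hardship group. On the plan's rates, 48.6% of non-reporters and 19.9% of reporters die within the year. The documents do not support using those figures here. Section 10.2 ends caregiver forms at patient death, so a patient who dies before month 6 has no follow-up caregiver score and drops out of a month-6 or month-12 comparison. Such patients enter only if baseline scores are the outcome or visits are pooled. The text does not exclude either, but states neither.

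Third, a reader might infer that the comparison is pushed towards no association or a reversed one. That needs independence of hardship and death, whereas Section 7.2 itself ties hardship to poor prognosis. With a shared frailty the gap vanishes or reverses, so no direction can be claimed.

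Fourth, the analysis is optional, secondary and largely descriptive, and the possible bias is small. Suppose about 105 caregivers at month 6, split 35:65, with SD 4 to 6 (all assumptions). The standard error is SD × √(1/37 + 1/68), about 0.8 to 1.2 points. An assumed strain excess of 3 to 6 points times 0.098 gives 0.3 to 0.6 points. This stands, and it sets the priority. It does not excuse leaving the visit and the exposure window unstated in a comparison that carries a stated expectation and, for burden, a named test.

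**Conclusion.** The concern holds as one of definition and method. Both caregiver comparisons lack a visit and a hardship cut-off, and neither uses the baseline caregiver score, although the plan handles the same exposure more carefully for HRQOL. On the any-report reading, exposure at month 6 depends on later reports and later survival: about 38% late first reports, and deaths in months 6 to 12 of about 16% against 26%. Those figures rest on the plan's rates, exponential times, and independence of hardship and death.

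It does not follow that early deaths are counted as no hardship in the follow-up comparisons, or that the result is biased in a known direction. The size also needs a strain difference that the documents do not give. The priority is low: this is a minor improvement to a largely descriptive secondary analysis.

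**What to change.** In Sections 7.2 and 7.3:
- Name the caregiver visit for each comparison.
- Classify hardship only from patient forms up to that visit. For the month-6 score, use month 3 alone or months 3 and 6, chosen in advance; month 3 alone keeps the exposure-before-outcome order of the HRQOL analysis. For the month-12 score, use forms up to month 12.
- Include patients on study with a caregiver form at that visit.
- Compare strain by linear regression and high burden by logistic regression, each adjusted for the baseline caregiver value.
- Report how many caregiver scores at each visit are missing because the patient died.

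At month 12 this matches the any-report grouping among patients still on study. The gain there is a stated rule and baseline adjustment. At month 6 it stops later reports from defining exposure. It does not remove a real association between hardship and prognosis, and the text should say so.

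The cost is wording; no new data are needed. Hardship first reported after month 6 no longer counts as exposure for the month-6 score, and caregivers without a baseline value drop out of the adjusted models.

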7.4 Data and Safety Monitoring Committee

There is no formal data and safety monitoring committee for this study. Monitoring of study conduct and accrual for feasibility will be performed routinely by the Study Coordinator, Study Statistician, and the Disease Committee Chair. Accrual reports are generated weekly.

8.0 REGISTRATION GUIDELINES

8.1 Registration Timing

Registration must be within 120 days after diagnosis of metastatic colorectal cancer. Treatment must start \leq 30 days after registration or must have been initiated \leq 60 days prior to registration.

8.2 Investigator/Site Registration

Prior to the recruitment of a patient for this study, investigators must be registered members of a NCTN Group. Each investigator must have an NCI investigator number and must maintain an "active" investigator registration status through the annual submission of a complete investigator registration packet to CTEP.

a. CTEP Investigator Registration Procedures

Food and Drug Administration (FDA) regulations and National Cancer Institute (NCI) policy require all investigators participating in any NCI-sponsored clinical trial to register and to renew their registration annually.

Registration requires the submission of:

- a completed Statement of Investigator Form (FDA Form 1572) with an original signature
- a current Curriculum Vitae (CV)
- a completed and signed **Supplemental Investigator Data Form** (IDF)
- a completed *Financial Disclosure Form* (FDF) with an original signature

Fillable PDF forms and additional information can be found on the CTEP website at http://ctep.cancer.gov/investigatorResources/investigator-registration.htm.

For questions, please contact the *CTEP Investigator Registration Help Desk* by email at cpnci.nih.gov.

b. CTEP Associate Registration Procedures

The Cancer Therapy Evaluation Program (CTEP) Identity and Access Management (IAM) application is a web-based application intended for use by both Investigators (i.e., all physicians involved in the conduct of NCI-sponsored clinical trials) and Associates (i.e., all staff involved in the conduct of NCI-sponsored clinical trials).

Associates will use the CTEP-IAM application to register (both initial registration and annual re-registration) with CTEP and to obtain a user account.

Investigators will use the CTEP-IAM application to obtain a user account only. (See CTEP Investigator Registration Procedures above for information on registering with CTEP as an Investigator, which must be completed before a CTEP-IAM account can be requested.)

An active CTEP-IAM user account will be needed to access all CTEP and CTSU (Cancer Trials Support Unit) websites and applications, including the CTSU members' website.

Additional information can be found on the CTEP website at http://ctep.cancer.gov/branches/pmb/associate_registration.htm. For questions, please contact the *CTEP Associate Registration Help Desk* by email at ctep.nci.nih.gov>.

c. CTSU Registration Procedures

This study is supported by the NCI Cancer Trials Support Unit (CTSU), but it is not under the purview of the DCP CIRB.

1. IRB Approval:

Each investigator or group of investigators at a clinical site must obtain IRB approval for this protocol and submit IRB approval and supporting documentation to the CTSU Regulatory Office before they can be approved to enroll patients. Assignment of site registration status in the CTSU Regulatory Support System (RSS) uses extensive data to make a determination of whether a site has fulfilled all regulatory criteria including but not limited to: an active Federal Wide Assurance (FWA) number, an active roster affiliation with the Lead Network or a participating organization, a valid IRB approval, and compliance with all protocol specific requirements.

2. Downloading Site Registration Documents:

Site registration forms may be downloaded from the \$1417CD protocol page located on the CTSU members' website.

- Go to https://www.ctsu.org_and log in to the members' area using your CTEP-IAM username and password
- Click on the Protocols tab in the upper left of your screen
- Either enter the protocol # in the search field at the top of the protocol tree, or
- Click on the By Lead Organization folder to expand
- Click on the SWOG link to expand, then select trial protocol

S1417CD

• Click on LPO Documents, select the Site Registration documents link, and download and complete the forms provided.

3. Requirements For S1417CD Site Registration:

- CTSU IRB Certification
- CTSU IRB/Regulatory Approval Transmittal Sheet

4. Submitting Regulatory Documents:

Submit forms and documents to the CTSU Regulatory Office via the Regulatory Submission Portal, where they will be entered and tracked in the CTSU RSS.

Regulatory Submission Portal: www.ctsu.org (members' area) → Regulatory Tab → Regulatory Submission

When applicable, original documents should be mailed to:

CTSU Regulatory Office [name]

Institutions with patients waiting that are unable to use the Portal should alert the CTSU Regulatory Office immediately at [contact] in order to receive further instruction and support.

5. Checking Your Site's Registration Status:

You can verify your site registration status on the members' section of the CTSU website.

- Go to https://www.ctsu.org and log in to the members' area using your CTEP-IAM username and password
- Click on the Regulatory tab at the top of your screen
- Click on the Site Registration tab
- Enter your 5-character CTEP Institution Code and click on Go

Note: The status given only reflects compliance with IRB documentation and institutional compliance with protocol-specific requirements as outlined by the Lead Network. It does not reflect compliance with protocol requirements for individuals participating on the protocol or the enrolling investigator's status with the NCI or their affiliated networks.

